### **6.1.3. Study Time Intervals**

To calculate the length of any time interval or time period in this study, the following formula will be used:

$$\text{Length of interval (days)} = \text{End Date} - \text{Interval Start Date} + 1$$

To convert any time length from days to weeks, the following formula will be used:

$$\text{Length of interval (weeks)} = \text{Length of interval (days)}/7$$

Only for the purpose of calculating the length of study period time intervals, the words “prior to” in [Table PYAD.6.2](#) should be understood to mean “the day before” while the words “after” should be understood to mean “the day after.” For the purpose of determining whether a date/time lies within an interval, these words are intended to convey whether the start or end of the period is inclusive of the specified date.

For the purposes of the endpoints assessing the incidence of SARS-CoV-2 infection, the words “by Day 29” should be understood to mean “at any time prior to and including the Day 29 visit, provided the visit occurs within the specified visit window.” The words “by Day 57” should be understood to have a similar meaning. For all other endpoints, similar definitions will apply, but results from visits outside of the specified visit window may be used.

**Table PYAD.6.2. Definition of Study Period Time Intervals**

Study Period	Interval Start Definition	Interval End Definition
Screening: All patients who sign informed consent are considered as entering the Screening Period.	Informed consent date	Prior to the start of Evaluation Period.
Evaluation Period: All patients who are randomized to the study are considered as entering the Evaluation Period.	At the start of study drug administration date/time following randomization. For patients who are randomized but not dosed, the Evaluation Period starts on the date of randomization.	The minimum of Evaluation Period discontinued date, study discontinuation date, or first Follow-Up visit date.
Follow-Up: All patients who had a follow up visit are considered as entering follow-up period.	After the Evaluation Period ends.	The maximum of the last study visit date or study disposition date.

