Part 3 objectives are exploratory and therefore described in [Section 3](#).

Overall Design

Study J2X-MC-PYAD is a randomized, double-blind, placebo-controlled, prophylaxis study to evaluate the efficacy and safety of intravenous LY3819253, alone and in combination with LY3832479, in preventing SARS-CoV-2 infection and COVID-19, compared to placebo. An independent Data Safety Monitor Board (DSMB) will actively monitor interim data to make recommendations about early study closure or changes to sample size.

Disclosure Statement: This is a three-part, 9-arm interventional study that is double-blinded.

Number of Participants:

For Part 1, a total of approximately 1700 participants (intent-to-treat [ITT] population) will be randomly assigned to study intervention such that approximately 1300 SARS-CoV-2 RT-PCR and serology negative participants are randomized in the study with the goal of achieving approximately 33 events (in each of the primary and key secondary endpoints) in the prevention population.

For Part 2, a total of approximately 2000 participants will be randomly assigned to study intervention based on rapid point of care (POC) testing such that approximately 1700 participants SARS-CoV-2 RT-PCR and serology negative participants are randomized in the Prevention Cohort with the goal of achieving approximately 56 events on each of the primary and key secondary endpoints.

Part 3 will enroll at least 30 participants and up to approximately 500 participants randomized to study intervention.

The maximum sample size for this study is approximately 5000 participants in the ITT population.

Intervention Groups and Duration:

Participants will receive one intravenous infusion of study intervention.

The maximum total duration of study participation for each participant of the prevention groups is 24 weeks.

The maximum total duration of study participation for each participant of the treatment group is 12 weeks.

Part 1:

Eligible participants will be randomized to one of two arms: placebo or LY3819253 4200 mg.

Participants will continue to enroll to Part 1 until the needed events for the primary and key secondary endpoints are achieved and the minimum number of residents enroll.

The evaluation period for Part 1 is 8 weeks, with follow-up to 24 weeks.

Part 2:

The Sponsor will decide when to trigger activation of Part 2. Activation of Part 2 will be communicated to sites.

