4.1.2. Evaluation Period

The evaluation period begins when the participant completes screening and is enrolled in the study. Assessments and procedures will be conducted as described in the SoA (Section [1.3](#)).

Participants in Part 1 will be randomized to placebo or LY3819253. The Sponsor will decide when to trigger activation of Part 2. Activation of Part 2 will be communicated to sites.

Participants in Part 2 will be assigned to a cohort as follows:

- Prevention Cohort: Participants who are SARS-CoV-2 negative during screening on the POC test will be randomized to one of three arms: placebo, LY3819253 700 mg, or LY3819253 350 mg + LY3832479 700 mg.
If enrolling to a placebo-controlled trial is challenged by an effective medication becoming available for prevention of COVID-19 and SARS-CoV-2, then the placebo arm may be dropped.

Note: It is possible that some participants have SARS-CoV-2 negative result on the screening point of care test, but could be positive on the baseline SARS-CoV-2 PCR test. The results from the baseline test will not be available until after the participant is randomized. Once positive results are known from the baseline test, these participants will be unblinded and have the option to continue to be followed for safety according to the Prevention Cohort SoA. Unblinded participants will not be included as part of the defined prevention population

The evaluation period for the Prevention Cohort is 8 weeks, with follow-up to Day 169.

- Treatment Cohort: Participants who test SARS-CoV-2 positive during screening with the POC test will be randomized to one of two arms: LY3819253 700 mg, or LY3819253 700 mg + LY3832479 1400 mg.

The evaluation period for the Treatment Cohort is 4 weeks, with follow-up to Day 85.

Participants in Part 3 will be randomized to LY3819253 700 mg or LY3819253 700 mg and LY3832479 1400 mg. The evaluation period for Part 3 is 4 weeks, with follow-up to Day 85. The Sponsor will decide when to trigger activation of Part 3. Activation of Part 3 will be communicated to sites. Part 3 may be activated prior to Part 2.

Part 2 and Part 3 could be activated concurrently. However, Part 3 will not enroll concurrently with Part 2 at the same facility.

Participants will receive one intravenous infusion of study intervention.

The maximum total duration of study participation for each participant of the prevention groups is 24 weeks. See the SOA for prevention groups in Section 1.3.1.

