### **5.1.3. Follow-up Period**

For Part 1 and for the Prevention Cohort in Part 2, post-treatment follow-up assessments will be conducted at Days 85, 141, and 169 according to the SoA.

For the Treatment Cohort in Part 2 and for all participants in Part 3, a post-evaluation follow-up assessment will be conducted at Day 85 according to the SoA.

Strategies to manage infection risks and reduce the burden of return visits may be used by sites, such as remote visits.

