### ***6.3.2. Missing COVID-19 Status or Disease Severity***

For the primary and key secondary endpoints, if a participant has at least one post-baseline RT-PCR test result and has not yet met the criterial for COVID-19 or is missing data used to determine COVID-19 status, the participant will be treated as not experiencing COVID-19. The same logic will be used for moderate-or-worse severity COVID-19.

As a supplementary analysis on these endpoints, the approach described in Section [6.3.1](#) will be used to handle missing COVID-19 status or disease severity due to death unrelated to COVID-19, study discontinuation, or the triggering of the Primary Database Lock. Participants with missing information will be treated as not experiencing the associated endpoint event and will be weighted based on the proportion of the Evaluation Period that was completed.

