#### **6.10.3.4. Hospitalization or Death Due to COVID-19 by Day 57**

The proportion of patients who experience hospitalization or death due to COVID-19 during the Evaluation Period will be summarized for participants in the Prevention population. In addition, the number of patients that experience hospitalization or death due to COVID-19 will be analyzed using logistic regression to compare each study intervention versus placebo, if there are sufficient data available. Statistical comparisons will be done using a logistic regression model. The model will include treatment, facility, role within the facility (resident vs staff) and sex as fixed effects. Missing data will be imputed using the NRI method as described in Section 6.3.3.

A listing of hospitalization status during the Evaluation Period will be created.

As an exploratory analysis, this analysis will be repeated on participants in the Treatment populations. Additionally, at each End of Evaluation Database Lock, the number of patients who are hospitalized or have died due to COVID-19 anytime after randomization will be analyzed to compare each study intervention versus placebo in the Prevention and Treatment populations, if there are sufficient data available.

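### SAP Table PYAD.6.2 runs a completer's Evaluation Period to the Day 85 follow-up visit, against 8 or 4 weeks in the protocol; one secondary analysis and several exploratory and safety analyses inherit the wrong window

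*SAP*

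**What the plan says.** - **SAP 6.1.3, Table PYAD.6.2.** The Evaluation Period ends at "The minimum of Evaluation Period discontinued date, study discontinuation date, or first Follow-Up visit date". The Follow-Up interval starts "After the Evaluation Period ends". No Day 57 or Day 29 limit appears in the table.
- **SAP 5.1.3.** For Part 1 and the Part 2 Prevention Cohort, "post-treatment follow-up assessments will be conducted at Days 85, 141, and 169". For the Part 2 Treatment Cohort and Part 3 the only follow-up visit is Day 85. The schedules of activities give that visit a window of 7 days either way.
- **Protocol 1.1 and 4.1.2.** "The evaluation period for Part 1 is 8 weeks, with follow-up to 24 weeks"; "The evaluation period for the Prevention Cohort is 8 weeks, with follow-up to Day 169"; "The evaluation period for the Treatment Cohort is 4 weeks, with follow-up to Day 85". Part 3 also has 4 weeks. Protocol 4.1.3 treats Day 85 as a post-evaluation visit.
- **SAP 6.10.3.4.** The heading says Day 57, but the text counts "hospitalization or death due to COVID-19 during the Evaluation Period".
- **SAP 6.3.2.** In the supplementary analysis of COVID-19 and of moderate-or-worse COVID-19, participants with missing information "will be weighted based on the proportion of the Evaluation Period that was completed". No day limit is given. The corresponding infection weight in 6.3.1 is limited to Day 29.

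**The concern.** The table is the SAP's only formal definition of the interval, so a programmer following it would include the Day 85 visit and everything before it in the Evaluation Period. That contradicts the protocol and, for hospitalization or death, the SAP's own heading.

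The extra weeks differ in kind from the planned ones. The dose rationale for Part 1 (protocol 4.3) aims at coverage for a minimum of 8 weeks in 90% of participants. Vaccination is discouraged only before Week 8 in the Part 2 Prevention Cohort (protocol 6.5). Daily collection runs to Day 57 in the prevention groups. In the treatment groups it covers hospitalized participants only, Days 2 to 29 (protocol 4.1.2). Worst NIAID score uses daily values, so the added days could bring in imputed scores under SAP 6.3.6 where no daily data were scheduled.

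**Working it through.** **1. The protocol's lengths.** SAP 6.1.3 defines length as end minus start plus 1, and weeks as days divided by 7. With the start at Day 1:

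| End | Days | Weeks | Protocol |
|---|---|---|---|
| Day 57 visit | 57 − 1 + 1 = 57 | 8.14 | 8 weeks: agrees |
| Day 29 visit | 29 − 1 + 1 = 29 | 4.14 | 4 weeks: agrees |
| Day 85 visit (table, completer) | 85 − 1 + 1 = 85 | 12.14 | agrees with neither |

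**2. Size of the excess.** Against Day 57: 85 − 57 = 28 days (21 to 35 for a visit on Day 78 to 92), ratio 85/57 = 1.49. Against Day 29: 85 − 29 = 56 days (49 to 63), ratio 85/29 = 2.93. The Part 1 Treatment population has an 8-week frame in protocol Section 3, so its comparison is Day 57.

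**3. Two boundary cases.** In the Part 2 Treatment Cohort and Part 3, Day 85 is the last scheduled visit. Follow-Up would then start on Day 86 and have length 85 − 86 + 1 = 0 days. In a prevention group, a participant who misses Day 85 has a first follow-up visit at Day 141, and the Evaluation Period stretches to there.

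**4. Which analyses use the interval.**

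- *Fixed by day, not affected:* the primary endpoint (6.10.1); both key secondary endpoints (6.10.3.1, 6.10.3.2); infection by Day 57 (6.10.3.3); deterioration and COVID-19 mortality in the Prevention populations (6.10.3.5, 6.10.3.6); the infection weight (6.3.1). No sample-size input uses the interval.
- *Tied to the Evaluation Period:* the text of 6.10.3.4, although protocol 9.4.6 sets 8 weeks; hospitalization or death, deterioration and COVID-19 death in the Treatment populations, although protocol Section 3 sets 4 weeks for Parts 2 and 3 and 8 weeks for Part 1; worst NIAID score (6.16.1.2) and NIAID worsening (6.16.2.2); viral load change (6.16.2.1); censoring for time to improvement, clearance, hospitalization and ICU admission (6.16.1.1, 6.16.1.4, 6.16.2.3, 6.16.2.4); the summaries in 6.12.5; and the timing of the End of Evaluation Database Locks (6.1.5).

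**5. The 6.3.2 weights.** The table ends the period at discontinuation. If that realised interval were the denominator, a participant who discontinues at Day 29 would get 29/29 = 1, and so would every other discontinuer; the weighting would do nothing for them. With the planned length to Day 57 the weight is 29/57 = 0.509.

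Illustration with assumed inputs: 650 per arm (half of 1300), 4.0% on placebo, 0.33 × 4.0% = 1.32% on active, and 20% of non-events in each arm discontinued at Day 29. On placebo there are 26 events and 624 non-events, of which 124.8 are incomplete. With weight 1 the placebo rate is 26/650 = 4.00%. With weight 0.509 it is 26/(26 + 499.2 + 63.5) = 4.42%. The odds ratio is 0.321 both ways, because incompleteness was assumed equal in the two arms.

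**The case against.** **The discontinued date could be read as a disposition date that includes completion.** SAP 6.6 does speak of evaluation-period disposition, and on that reading the end would fall near Day 57 or Day 29. The text does not carry it. The Follow-Up row of the same table uses the term disposition date, while the Evaluation row uses discontinuation terms. SAP 6.1.5 also separates completing the Evaluation Period from discontinuing. Nothing defines a date for completers.

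**The intended windows are clear elsewhere.** The protocol's objective tables give 8-week and 4-week frames, its schedules place Day 85 outside the evaluation columns, and SAP 5.1.3 itself calls Day 85 post-evaluation for the Part 2 Treatment Cohort and Part 3. This settles the intention and makes the correction easy. It does not remove the conflict, because the SAP does not say that those frames override its table.

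**Nothing confirmatory depends on this.** That stands. In the balanced illustration the odds ratio does not move, and no bias in a treatment comparison has been shown.

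Some stronger readings are tempting but unsupported:

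- *A participant past Day 57 but short of Day 85 at the lock is weighted 57/85 = 0.67.* A reader might infer this. SAP 6.3.2 weights only participants whose status is missing, and someone complete through Day 57 has no missing status on a Day 57 endpoint. Nor does the SAP state 85 days as a planned denominator.
- *All supplementary weights are affected.* The infection weight is already limited to Day 29.
- *Later events go unobserved.* Hospitalization events are also scheduled for recording at Day 85; what ends earlier is daily collection.

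**Conclusion.** The concern holds with limited scope. Followed as written, Table PYAD.6.2 gives a completer an 85-day Evaluation Period where the protocol intends 57 or 29 days, about 1.5 or 2.9 times as long. It is a wrong rule, not merely a missing detail, because it sets a definite date that contradicts the protocol. The most important analysis it reaches is the protocol-listed secondary endpoint of hospitalization or death; the rest are supplementary, exploratory or descriptive. The End of Evaluation locks would also wait about four weeks longer in the prevention groups.

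A reader might infer that the trial's main result is assessed over the wrong period. It is not: the primary and key secondary windows are stated by day. The conclusion assumes that the discontinuation dates are blank for completers and that the first follow-up visit is the scheduled Day 85 visit. Participants who discontinue earlier are unaffected by the Day 85 term, although the 6.3.2 denominator still needs stating for them.

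**What to change.** Make three wording changes in the SAP, preferably before the affected outputs are run on unblinded data:

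1. **Table PYAD.6.2.** End the Evaluation Period at the earliest of Evaluation Period discontinuation, study discontinuation, or the Day 57 visit (Part 1 and Part 2 Prevention Cohort) or Day 29 visit (Part 2 Treatment Cohort and Part 3). Use the nominal day if that visit is missed.
2. **Section 6.10.3.4.** For the Prevention populations, count events by Day 57 in the text, matching the heading. The Treatment populations then follow their corrected periods: Day 57 in Part 1, Day 29 in Parts 2 and 3.
3. **Section 6.3.2.** State that the weight is days completed divided by the fixed planned length to Day 57, whatever the reason for incompleteness.

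The cost is one table cell, one phrase and one sentence. No new data are needed, and the primary test, sample size and power do not change. The other listed analyses correct themselves once the table is corrected.

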#### **6.1.4. Analysis Methods**

Unless otherwise specified, variables will be analyzed in the original scale on which they are measured. SARS-CoV-2 viral load data will be evaluated in log base 10 scale. The parametric approach will be employed by default for statistical analysis except when nonparametric analysis, such as by a rank-based method, Mann-Whitney, or van Elteren tests, is deemed to be more appropriate.

Parts 1 and 2 of the study will each have an experiment-wise error rate of 0.05 for the primary and key secondary endpoints. A graphical testing sequence strategy will be used to adjust for multiplicity in the primary and key secondary endpoints within each part of the study. All other hypothesis tests will be conducted at a 2-sided alpha level of 0.05.

Any change to the data analysis methods described in the protocol will require an amendment only if it changes a principal feature of the protocol. Additional exploratory analyses of the data may be conducted as deemed appropriate.

For analyses on the Part 2 Prevention population, LY3819253-700mg and LY3819253-350mg+LY3832479-700mg will be assessed against placebo separately.

**Table PYAD.6.3. Tables and Figures Related to Demographics and Other Characteristics of Study Population**

Method	Analysis
Descriptive Statistics	Number of participants, mean, standard deviation, median, minimum, maximum, and 10 th and 90 th percentiles for continuous measures, and frequency counts and percentages for categorical measures
Kaplan-Meier curves and summary statistics, Cox proportional hazards	Treatment comparisons of time-to-event based endpoints
Logistic regression analysis	Treatment comparisons of binary variables with treatment, facility, and randomization stratification variables in the model

Nonparametric (e.g., Mann-Whitney or van Elteren tests)	Treatment comparison of ordinal, nominal, and non-normally distributed continuous variables
Mixed-effects model repeated measures (MMRM) analysis	Treatment comparisons of continuous efficacy and health outcome variables
Chi-square test or Fisher's exact test	Treatment comparison of binary endpoints

Treatment comparisons of continuous safety variables with multiple postbaseline measurements will be made using MMRM analysis. When MMRM is used, it includes: (a) treatment group, (b) facility, (c) role within the facility (resident vs staff), (d) sex, (e) baseline value in the model, (f) visit, and (g) the interactions of treatment-by-visit as fixed factors, and the patient as a random effect. The covariance structure to model the within-patient errors will be unstructured. If the unstructured covariance matrix results in a lack of convergence, the heterogeneous Toeplitz covariance structure, followed by the heterogeneous autoregressive covariance structure, will be used. The first structure to yield convergence will be used for inference. The Kenward-Roger method will be used to estimate the denominator degrees of freedom. Type III sums of squares for the least-squares (LS) means will be used for the statistical comparison; the 95% confidence interval (CI) will also be reported. Unless otherwise specified, for MMRM, reported data from only planned visits will be used as the primary analysis.

Treatment comparisons of continuous efficacy and safety variables with a single postbaseline timepoint will be made using analysis of covariance (ANCOVA) with: (a) treatment group, (b) facility, (c) role within the facility (resident vs staff), (d) sex and (e) baseline value in the model. Type III sums of squares for LS means will be used for statistical comparison between treatment groups. The LS mean difference, standard error, p-value-, and 95% CI, unless otherwise specified, will also be reported. Missing data imputation method for the ANCOVA model is specified in Section 6.3.

Treatment comparisons for binary efficacy endpoints will be made using logistic regression. The model will include the treatment groups, facility, and the stratification factors (resident/staff and sex) as explanatory variables. For the primary and key secondary endpoints, p-values from Rao's score test (or score test) will be reported (Rao 1948). For all other endpoints, results from a Wald test will be reported. The odds ratio and the corresponding CIs, as well as the treatment differences and the corresponding CIs, will be reported.

For other binary endpoints, treatment comparisons will be made using Chi-square tests if the expected count is at least 5 in at least 80% of the cells, otherwise a Fisher's exact Test will be used.

The Kaplan-Meier (KM) product limit method will be used for time-to-event analyses. The hazard ratio and log-rank test will be reported. Time for all analyses will be described in units of days.

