**Figure PYAD.6.1. Graphical testing scheme for the primary and key secondary endpoints in Part 1**

For Part 2, the graphical approach shown in [Figure PYAD.6.1](#) will be repeated to compare LY3819253-350mg+LY3832479-700mg versus placebo. If all three endpoints are successful, the testing scheme will then be repeated to compare LY3819253-700mg versus placebo.

All other analyses will be conducted at the two-sided 0.05 significance level without adjustments for multiplicity.

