#### 6.10.3.5. COVID-19-Related Deterioration (Hospitalization, Emergency Room, or Death by Day 57)

Proportion (percentage) of participants who experience deterioration by Day 57 will be analyzed and is defined as:

- COVID-19-related hospitalization (defined as  $\geq 24$  hours of acute care)
- a COVID-19-related emergency room visit, or
- death related to COVID-19

The proportion of patients that experience deterioration by Day 57 will be summarized by treatment group in frequency tables and listed for participants in the Prevention Population.

In addition, the number of patients that experience deterioration by Day 57 will be analyzed using logistic regression to compare each study intervention versus placebo, if there are sufficient data available. Statistical comparisons between each study intervention and placebo will be done using a logistic regression model. The model will include treatment, facility, role within the facility (resident vs staff) and sex as fixed effects. Missing data will be imputed using the NRI method as described in Section 6.3.3.

As an exploratory analysis, this analysis will be repeated on participants in the Treatment populations for events of deterioration up to the end of their respective Evaluation Periods.

#### 6.10.3.6. COVID-19-Related Mortality by Day 57

The proportion of patients that experience death due to COVID-19 by Day 57 will be summarized by treatment in frequency tables and listed for participants in the Prevention Populations.

In addition, the number of patients that experience death due to COVID-19 by Day 57 will be analyzed using logistic regression to compare each study intervention versus placebo, if there are sufficient data available. Statistical comparisons between each study intervention and placebo will be done using a logistic regression model. The model will include treatment, facility, role within the facility (resident vs staff) and sex as fixed effects. Missing data will be imputed using the NRI method as described in Section 6.3.3.

As an exploratory analysis, this analysis will be repeated on participants in the Treatment populations for deaths due to COVID-19 by the end of their respective Evaluation Periods.

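### Wald results are planned for rare non-key secondaries such as COVID-19 death, and the SAP names no fallback if the active arm has no events

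*SAP*

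**What the plan says.** SAP 6.1.4 analyses binary efficacy endpoints by logistic regression: "The model will include the treatment groups, facility, and the stratification factors (resident/staff and sex) as explanatory variables". It then splits the inference in two. For the confirmatory endpoints, "For the primary and key secondary endpoints, p-values from Rao's score test (or score test) will be reported". For the rest, "For all other endpoints, results from a Wald test will be reported". The same paragraph also asks for odds ratios and treatment differences, each with confidence intervals.

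Three rarer secondaries fall under the Wald rule: hospitalization or death due to COVID-19 (SAP 6.10.3.4), COVID-19-related deterioration (6.10.3.5) and COVID-19-related mortality (6.10.3.6). For mortality, "the number of patients that experience death due to COVID-19 by Day 57 will be analyzed using logistic regression to compare each study intervention"; placebo is the comparator, and treatment, facility, role and sex enter as fixed effects. All three analyses carry the condition "if there are sufficient data available". No event count defines it, and no alternative is named if it fails.

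A chi-square or Fisher rule does exist in 6.1.4, but it is introduced separately: "For other binary endpoints, treatment comparisons will be made using Chi-square tests if the expected count is at least 5" (in most cells). It follows the paragraph on binary efficacy endpoints, and 6.10.3.4 to 6.10.3.6 name logistic regression explicitly. SAP 6.5 places these secondaries outside multiplicity control: "All other analyses will be conducted at the two-sided 0.05 significance level without adjustments for multiplicity".

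**The concern.** The plan gives the test that tolerates a zero cell to the commoner outcomes and the one that does not to the rarest. With no events in one arm, the fitted log odds ratio for treatment runs off towards minus infinity and its standard error grows much faster, so the Wald statistic shrinks to zero. More placebo deaths do not rescue it. The printed p-value is then set by the software's stopping rule and not by the data.

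At stake is how the odds-ratio comparison reads for mortality, which the protocol (Section 3) lists as an objective to be compared between arms in Part 1. A strong separation could appear next to a p-value near 1 and an unbounded interval. Alternatively, the comparison could be left out under a condition judged after the counts are known.

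**Working it through.** **Arm size.** The SAP gives no figure for these analyses, so I take the arm size from Part 1 (SAP 5.2: 33 events, about 1300 participants; protocol 6.3: 1:1 allocation) and first check that those figures cohere.

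- Schoenfeld: 4 × (1.960 + 1.282)² / (ln 0.33)² = 34.2 events. With the risk ratio of 0.33 at a 4.0% placebo rate expressed as an odds ratio (0.321), the result is 32.6, which rounds up to the stated 33.
- Mean event rate: (4.0% + 0.33 × 4.0%) / 2 = 2.66%. Then 1300 × 2.66% = 34.6 events, consistent with 33.
- Arm size: 1300 / 2 = 650.

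**Zero active events, k placebo events, unadjusted.** The score statistic is z = (k/650) / √[p(1 − p) × 2/650], with p = k/1300. For k = 8: p = 0.00615, difference 0.01231, standard error 0.00434, z = 2.84, two-sided p = 0.0046. The Wald column is from a Newton fit stopped at a relative gradient criterion of 1e-8.

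| Active vs placebo events | Score p | Fisher p | Wald p |
|---|---|---|---|
| 0 vs 3 | 0.083 | 0.249 | 0.995 |
| 0 vs 4 | 0.045 | 0.124 | 0.994 |
| 0 vs 5 | 0.025 | 0.062 | 0.993 |
| 0 vs 6 | 0.014 | 0.031 | 0.992 |
| 0 vs 8 | 0.0046 | 0.0076 | 0.994 |
| 0 vs 10 | 0.0015 | 0.0019 | 0.994 |

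At 0 vs 8 the fit stops at a log odds ratio of −17.7 with a standard error of about 2,460. Starting Newton from zero, the Wald p-value is 0.52, 0.93 and 0.99 after 10, 15 and 20 steps. No single value is the Wald p-value; only the limit of 1 is meaningful.

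**One active event.** The Wald result is then finite but weaker. For 1 vs 8: Wald 0.049, score 0.019, Fisher 0.038.

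**Facility adjustment.** The number of facilities is not stated. Assuming 65 facilities of 20 or 26 of 50, with one simulated data set per setting and 0 vs 4 to 10 deaths, Wald p was 0.993 to 0.997 and score p 0.0002 to 0.07. The pattern is unchanged.

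**Risk difference.** For 0 vs 8: −1.23%, standard error √(0.01231 × 0.98769 / 650) = 0.43%, 95% CI −2.08% to −0.38%. For 0 vs 5: −1.44% to −0.10%. Both are finite and exclude zero.

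**How often it would matter.** The death rate and the risk ratio for death are both assumptions. Let m be the expected placebo deaths and take a risk ratio of 0.33, with Poisson counts. P(0 active) = exp(−0.33m). A score p-value below 0.05 then needs at least 4 placebo deaths, and Fisher needs at least 6.

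| m | P(0 active) | × P(≥4 placebo) | × P(≥6 placebo) |
|---|---|---|---|
| 4 | 0.267 | 0.567 → 15.1% | 0.215 → 5.7% |
| 5 | 0.192 | 0.735 → 14.1% | 0.384 → 7.4% |
| 6 | 0.138 | 0.849 → 11.7% | 0.554 → 7.7% |

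**The case against.** The best defence is that little rests on this p-value. The primary and key secondary endpoints already use the score test. The affected endpoints are outside alpha control, and the efficacy ones appear as other secondaries for Part 1 only, since the corresponding Part 2 list is pharmacokinetic. SAP 6.1.4 requires treatment differences with intervals, and 6.10.3.4 to 6.10.3.6 require summaries of proportions, so 0 versus 8 deaths would be plain to any reader. All of that stands and limits the point.

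Four stronger readings are tempting, and the documents do not support them:

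- *The mortality evidence would be useless or reported as clearly negative.* Only the odds-ratio part fails; the risk difference at 0 vs 8 excludes zero.
- *The sufficient-data condition would remove the analysis whenever one arm has no events.* It is undefined, so it might do so or might not. The fair complaint is the missing threshold and fallback.
- *The chance of harm is 14% to 27%.* That is the chance of zero active events alone, including cases with too few placebo deaths for any test to reach 0.05. It also borrows a risk ratio that SAP 5.2 states only for the primary and key secondary endpoints.
- *All three secondaries are equally exposed.* The two composites include COVID-19 deaths, so they cannot have fewer affected participants than death alone.

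The condition can also be defended as a guard against fitting non-estimable models. That is its natural purpose, but 0 vs 10 could reasonably be judged sufficient, and Wald fails there too.

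**Conclusion.** The point holds in limited form. As written, the SAP attaches a Wald result to COVID-19 death and has no rule for a zero cell. With zero active deaths that result is uninformative at any number of placebo deaths, while the score test already used elsewhere in the SAP would work. The loss falls on nominal p-values, odds ratios and odds-ratio intervals; no confirmatory conclusion changes.

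The size depends on assumptions the documents do not supply: 4 to 6 expected placebo deaths and a risk ratio of 0.33 for death. On those, zero active deaths together with a score p-value below 0.05 has a chance of about 12% to 15%, or about 6% to 8% if the comparator is Fisher's test. The p-values rest on 650 per arm without covariates; the facility-adjusted check rests on assumed facility layouts. It is worth correcting because the correction is nearly free.

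**What to change.** In SAP 6.1.4, report Rao's score p-value for all binary efficacy endpoints, as already specified for the primary and key secondaries. When an arm has few or no events, report Firth-penalised, profile-likelihood or exact (facility-stratified) odds ratios and intervals in place of the Wald ones. State how facilities without any events are handled, since the fixed facility effects separate there as well.

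In 6.10.3.4 to 6.10.3.6, replace "if there are sufficient data available" with a pre-specified minimum total event count across arms that does not require any event on active treatment. A trigger of one event would be too low: 0 vs 1 gives a score p-value of 0.32 and a Fisher p-value of 1.0. At 1:1 with all events on placebo, four is the smallest total at which the score test can fall below 0.05, and six for Fisher, which gives a basis for choosing.

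The cost is a few lines of SAP text and a programming option. No new data or design change is needed. The rule should be fixed before unblinded data for the part concerned are seen.
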